9.6.3 Further safety

9.6.3.1 Endometrial biopsies

9.6.3.1.1 Algorithm for evaluation of endometrial safety

A careful endometrial safety monitoring is applied in this study which included regular ultrasound investigations during the active treatment period (see Section [9.6.3.11](#) for description of procedure), endometrial biopsies (see Section [9.6.3.1](#)), and observation of bleeding patterns (see Section [9.6.3.1.7](#)). With implementation of Protocol Amendment no. 7 one more examination is planned according to the algorithm below.

Figure 9–1: Overview of the endometrial safety monitoring algorithm

¹ Normal is defined as: Diagnosis of safety read and of all 3 individual components of the multiread needs to be "benign endometrium" in Part II of the evaluation form. In addition, the majority diagnosis needs to be "PAEC no" in Part IV of the evaluation form.

² Post-treatment is defined as biopsy taken at the earliest 7 days before last study drug intake.

9.6.3.1.2 Timing of last endometrial biopsy

Each subject should have an endometrial biopsy with a normal¹⁸ result documented from a timepoint after last study drug intake. For subjects with menstrual cycles the endometrial biopsy should be taken between Day 7 to 15 (inclusive) of a menstrual cycle.

Subjects who did not have such a biopsy before or during the temporary pause or those who have an abnormality in transvaginal ultrasound (TVU) and/or bleeding pattern are required to undergo an endometrial biopsy at the safety closeout visit.

The biopsy CRF page should be filled out for every subject at the safety closeout visit. This also applies to subjects who do not require a new biopsy according to the guidance above. The CRF page captures the reason why a biopsy was not done.

Depending on the result of this last scheduled endometrial biopsy, repeat unscheduled endometrial biopsies should be performed in addition. See Sections 9.6.3.1.5 and Figure 9–1 for details.

9.6.3.1.3 Sampling of endometrial biopsies

All endometrial biopsies must be collected by a gynecologically well experienced physician.

A negative pregnancy test is a prerequisite for performing an endometrial biopsy. In addition, an ultrasound should be performed before each biopsy.

If a cervical cytology sample is collected at the same visit, those procedures have to be performed before performing the biopsy.

The sterilized, disposable device Pipelle de Cornier will be used – a flexible and transparent polypropylene sheath with an internal plunger for aspiration. This device allows for gentle tissue sampling, without hysteroscopy, and generally requires no local anesthesia or cervical dilatation.

The following contraindications have to be strictly adhered to: pregnancy (ie, positive urine pregnancy test), and local inflammation (eg, vaginitis, cervicitis).

Any procedure-related complaints will be documented as AEs. If necessary for pain prophylaxis or relief relating to the endometrial biopsy procedure, the use of an analgesic is permitted and will be documented as concomitant medication (investigator's choice; however, no intake of acetylsalicylic acid or any other medication substantially influencing bleeding).

9.6.3.1.4 Assessment of endometrial biopsies

Blinding and distribution of biopsy samples will be organized by the central laboratory.

Central assessment of endometrial biopsies will be performed in 2 steps, i.e. safety assessment and multi-reader assessment. In cases where an abnormality, e.g. atypia or malignancy, cannot be ruled out, readers will select the most severe diagnosis.

¹⁸ Normal defined as: Diagnosis of safety read and of all 3 individual components of the multiread needs to be “benign endometrium” in Part II of the evaluation form. In addition, the majority diagnosis needs to be “PAEC no” in Part IV of the evaluation form.

Safety assessment

The safety assessment will be performed by one pathologist who will be blinded regarding treatment group. The results of the safety assessment need to be available in time to document:

- Any relevant pathology that requires further diagnostic or therapeutic measures according to local medical practice
- Absence of clinically relevant endometrial pathology before the subject leaves the study
- A repeat endometrial biopsy will be requested, if sample is inadequate for evaluation in the safety assessment.
- For follow-up of biopsies with abnormalities see Section [9.6.3.1.5](#).

Multi-reader assessment

The multi-reader assessment will be performed by a panel of pathologists who will be blinded regarding treatment group and time point of sample. This assessment will be performed as batch reads when a sufficient number of samples are available.

A majority consensus diagnosis of the multi-reader assessment is derived from the individual diagnoses of the pathologist panel (single-reader diagnoses), according to pre-specified rules. In the absence of a majority consensus, the most severe diagnosis is used. The derived diagnosis resulting from these rules will be used for primary analysis of endometrial biopsy data. The individual diagnoses of each reader will be captured in addition.

Starting with Protocol Amendment no. 7, the majority diagnosis of the multi-reader assessment (Part II of the evaluation form, i.e. the diagnoses benign endometrium, endometrial hyperplasia or malignant neoplasm) will be communicated to the study sites once the majority consensus diagnosis is available.

A repeat endometrial biopsy will be requested, if sample is inadequate for evaluation in the majority multi-reader assessment.

For follow-up of biopsies with abnormalities see Section [9.6.3.1.5](#).

Besides standard safety criteria (e.g., proliferative/secretory/atrophic endometrium, endometrial hyperplasia, malignant neoplasm) the pathologists will document the presence of PAEC (see Section [9.6.3.1.6](#)). The results of the PAEC assessment will not be reported back to the investigators except if in the last biopsy within the study, PAEC is still present and further biopsy sampling is needed.

The main study evaluation will be based on the majority diagnosis of the multi-reader assessment. An analysis of single-reader diagnoses that is more severe than the majority diagnosis will be provided in the Study Report. Investigators will be informed in addition about a single-reader diagnosis (Part II of the evaluation form) that is more severe than the majority diagnosis (Malignant neoplasm > Endometrial Hyperplasia > Benign endometrium).

While the relevant diagnosis for study purposes is the majority result of the multi-reader assessment, any single reader diagnosis that is more severe than the majority diagnosis should be evaluated by the investigator (or by a gynecologist in case the investigator or sub-investigator is not specifically trained in gynecology) for the necessity of therapeutic

interventions. The minimal diagnostic requirement for those cases is a follow up biopsy. For all follow-up examinations and/or therapeutic interventions all efforts should be taken that these examinations are conducted according to the standards of this protocol (e.g. biopsies should undergo multi-reader assessment) and are documented within the study framework.

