6.5 Withdrawal of subjects from study

6.5.1 Withdrawal

No longer valid, since with the implementation of Protocol Amendment no. 7 no subjects will start or continue treatment in this study.

Originally, the criteria for withdrawal from the study or from the study treatment were the following:

Subjects *must* be withdrawn from the **study** if any of the following occurs:

- At their own request or at the request of their legally acceptable representative. At any time during the study and without giving reasons, a subject may decline to participate further. The subject will not suffer any disadvantage as a result.
- At the specific request of the sponsor and in liaison with the investigator (eg, obvious non-compliance, safety concerns).
- Pregnancy, for further follow-up, see Section [9.6.2](#)
- Surgical treatment of endometriosis, for further follow-up, see Sections [9.7.2](#) and [9.6.1.4](#) (in case of an serious adverse event (SAE))
- If, in the investigator's opinion, continuation of the study would be harmful to the subject's well-being

Subjects *must* be withdrawn from **study treatment** if any of the following occurs:

- GPT/ALT or GOT/AST >8 x ULN
- GPT/ALT or GOT/AST >5 x ULN for more than 2 weeks
- GPT/ALT or GOT/AST >3 x ULN and total bilirubin >2 x ULN or international normalized ratio (INR) >1.5
- GPT/ALT or GOT/AST > 3 x ULN with the appearance of fatigue, nausea, vomiting, right upper abdominal quadrant pain or tenderness, fever, rash, and/or eosinophilia (>5%)
- Atypical hyperplasia, endometrial intraepithelial neoplasia (EIN) or malignant neoplasm
- Loss of BMD >6% at the lumbar spine compared to baseline accompanied by a Z-score reading of ≤ -2 SD (standard deviation) (determined either by the central reading imaging laboratory or by assessment at the site and confirmed by the

central reading imaging laboratory at the end of the 1st 6 months treatment period visit).

Subjects *may* be withdrawn from **study treatment** if any of the following occurs:

- Any of the inclusion criteria are no longer fulfilled
- Any of the exclusion criteria apply during treatment.

Screening failure

A subject who, for any reason (eg, failure to satisfy the selection criteria), terminated the study before randomization, is regarded a “screening failure”.

Dropout

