- The admission is pre-planned
(e.g. elective or scheduled surgery arranged prior to the start of the study; admission is part of the study procedures)
- The admission is not associated with an AE
(e.g. social hospitalization for purposes of respite care).

However, it should be noted that invasive treatment during any hospitalization may fulfill the criterion of ‘medically important’ and as such may be reportable as an SAE dependent on clinical judgment. In addition, where local regulatory authorities specifically require a more stringent definition, the local regulation takes precedence. All instances of liver parameter testing which meet criteria for withdrawal of a subject from the study treatment should be reported as SAE.

- d. Results in persistent or significant disability / incapacity

Disability means a substantial disruption of a person’s ability to conduct normal life’s functions.

- e. Is a congenital anomaly / birth defect
- f. Is another serious or important medical event (IME) as judged by the investigator

All instances of liver parameter testing which meet criteria for withdrawal of a subject from the study should be reported as SAEs.

Endometrial biopsies with a safety read diagnosis of “simple or complex atypical hyperplasia” (according to WHO 1994 criteria) or “EIN” (according to WHO 2014 criteria) (13) or in a diagnosis of “malignant neoplasm” (“endometrial” or “other”) should be reported as a serious adverse event. The subsequent multi-reader assessment should trigger a follow-up report and an update of the diagnosis should be considered, if the majority assessment is different from the initial safety read diagnosis.

Endometrial biopsies with a majority diagnosis based on the multi-reader assessment of “simple or complex atypical hyperplasia” (according to WHO 1994 criteria) or “EIN” (according to WHO 2014 criteria) or in a diagnosis of “malignant neoplasm” (“endometrial” or “other”) should be reported as a serious adverse event or trigger an update of the respective initial SAE report.

A diagnosis of an adrenal tumor needs to be reported as an SAE.

Any dermatology expert's diagnosis of a malignant skin lesion, including cutaneous sarcoma confirmed by biopsy diagnosis, needs to be reported as an SAE.

The following types of events are excluded from SAE reporting:

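### The severity order for single-reader biopsy notices, and the diagnosis sent to sites, do not carry the atypia/EIN split on which the SAE rule depends

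*Protocol*

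**What the plan says.** Protocol 9.6.3.1.4 sets up a panel read of each endometrial biopsy. From Amendment 7 on, sites receive the Part II majority diagnosis, "i.e. the diagnoses benign endometrium, endometrial hyperplasia or malignant neoplasm". The majority is derived by pre-specified rules that are not reproduced. For ties the text says: "In the absence of a majority consensus, the most severe diagnosis is used". It prints no severity order at that point.

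The same section adds a second message to sites: "Investigators will be informed in addition about a single-reader diagnosis (Part II of the evaluation form"), where that diagnosis is "more severe than the majority diagnosis (Malignant neoplasm > Endometrial Hyperplasia > Benign endometrium"). The investigator must then evaluate whether an intervention is needed, with a follow-up biopsy as the minimum. The Study Report is to analyse the same more-severe single reads.

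The SAE definition in 9.6.1.1 cuts at a different point. It covers "Endometrial biopsies with a majority diagnosis based on the multi-reader assessment of" atypical hyperplasia, EIN or malignant neoplasm, and applies the same criterion separately to the safety read. Hyperplasia without atypia is not in it. The treatment-withdrawal list in 6.5.1, no longer in force, drew the same line: "Atypical hyperplasia, endometrial intraepithelial neoplasia (EIN) or malignant neoplasm".

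Atypia is recognised elsewhere too. Section 9.6.3.1.4 names it beside malignancy when it tells readers to choose the most severe diagnosis in doubtful cases, and 9.6.3.1.5 describes hyperplasia as occurring with or without it. SAP 6.4 only lists endometrial histology as recorded.

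**The concern.** The SAE rule needs to know whether hyperplasia is atypical. The order that decides which lone read reaches the investigator, and the term sent to the site, have a single hyperplasia level.

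Two things follow on the text. First, a lone atypia/EIN read against a non-atypical hyperplasia majority is not more severe on the printed order. The investigator is not told of it, the evaluation for intervention is not triggered by it, and it drops out of the Study Report analysis of more-severe single reads. Second, a site that receives only the term endometrial hyperplasia cannot tell whether the majority meets the SAE rule. Nor can it tell whether the majority differs from an earlier atypical safety read, which 9.6.1.1 makes a reason to consider updating the diagnosis.

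Rodent endometrial adenocarcinoma is one of the findings behind the closeout (Section 3), and the output is listings only (10.1), so individual results carry the information.

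**Working it through.** The plan gives no figure to reproduce; the check is an enumeration.

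**Inputs**
- Panel of 3 readers: the definition of a normal biopsy (footnote in 9.6.3.1.2, note to Figure 9–1) refers to 3 components of the multiread.
- Majority, with the most severe diagnosis used if there is none: 9.6.3.1.4.
- Printed three-level order for the single-reader notice: 9.6.3.1.4.
- SAE if the majority is atypical hyperplasia/EIN or malignancy: 9.6.1.1.
- Assumption: readers can return four diagnoses, namely B (benign), H (hyperplasia without atypia), A (atypical hyperplasia/EIN) and M (malignant).

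**Step 1: all patterns.** Unordered results of 3 reads over 4 diagnoses: C(4 + 3 − 1, 3) = C(6, 3) = 20.

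**Step 2: patterns where the term sent settles the matter.** Pooling H and A, four patterns have a benign majority (BBB, BBH, BBA, BBM) and six give malignant by majority or tie-break (BHM, BAM, BMM, HMM, AMM, MMM). None of the four is a majority-based SAE and all six are. A lone A against two benign reads (BBA) is already flagged.

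**Step 3: patterns with a pooled hyperplasia majority.** At least two reads must be H or A. Exactly two: 3 pairs (HH, HA, AA) × 2 third reads (B, M) = 6. All three: 4 (HHH, HHA, HAA, AAA). Total 6 + 4 = 10. The result is then taken again with A ranked between H and M:

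| Reads | Pooled majority | Result with A as own level | Meets SAE rule | Notice, printed order | Notice, A as own level |
|---|---|---|---|---|---|
| BHH | hyperplasia | H | no | no | no |
| BHA | hyperplasia | A (tie-break) | yes | no | no |
| BAA | hyperplasia | A | yes | no | no |
| HHH | hyperplasia | H | no | no | no |
| HHA | hyperplasia | H | no | no | **yes** |
| HAA | hyperplasia | A | yes | no | no |
| AAA | hyperplasia | A | yes | no | no |
| HHM | hyperplasia | H | no | yes (M read) | yes (M read) |
| HAM | hyperplasia | M (tie-break) | yes | yes (M read) | no (M is the result) |
| AAM | hyperplasia | A | yes | yes (M read) | yes (M read) |

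**Step 4: SAE count.** Six of the 10 meet the rule and four do not. In four of the six (BAA, HAA, AAA, AAM) at least two readers call atypia outright. The other two (BHA, HAM) depend on the level at which the majority is taken.

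**Step 5: notice count.** In none of the 10 does an A read rank above the pooled majority. HHM, HAM and AAM are flagged only through their M read. With A as its own level, the one notice gained is HHA.

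**The case against.** The strongest reply is that little clinical protection is missing. A reader might infer that the follow-up biopsy is lost in the HHA case. It is not: 9.6.3.1.5 already calls for biopsies until resolution, or an intervention, for any hyperplasia majority, which is at least what the single-reader rule requires. That part of the reply stands in full.

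A reader might also infer that a lone atypia read is a missed SAE. It is not, because under 9.6.1.1 only the safety read and the majority trigger an SAE, and in HHA the majority is non-atypical on either scale.

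A third inference would be that the majority and tie-break are themselves run on three levels, so that SAE status is wrong in BHA and HAM. The documents do not show this. The three-level order is printed only for the single-reader notice, the majority rules are not included, and 9.6.1.1 speaks of a majority of atypical hyperplasia, which implies that one can be formed. In HAM the malignant read is in any case passed on under the printed order.

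There are partial safeguards: the separate SAE trigger on the safety read, the expedited multi-read when that read is not benign, AESI status for all hyperplasia (9.6.1.6), and capture of every reader's diagnosis. The safety read helps only if that one pathologist calls atypia, and AESI status does not replace the SAE rule. The evaluation form may hold an atypia field, but neither document says that it is sent to sites or used in the order.

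**Conclusion.** The mismatch is real on the text. The single-reader order hides a lone atypia/EIN read against a non-atypical hyperplasia majority, and the communicated term covers both SAE and non-SAE results: 6 and 4 of 10 patterns if atypia is its own level in the majority. What is lost is information: the notice, the evaluation it prompts, its place in the Study Report analysis, and the site's means of applying the SAE rule.

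The counts rest on three readers and four distinguishable diagnoses. They say nothing about how often a pattern occurs. Stronger statements, that biopsies are omitted or that SAE status is shown to change, are not supported. With 8 of 315 planned subjects enrolled (Section 3), and the closeout evaluation limited to those who took vilaprisan, the practical effect is small. The point still merits correction because it concerns a main closeout safety question and is cheap to settle.

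**What to change.** Reconcile 9.6.1.1, 9.6.3.1.4 and 9.6.3.1.5. State that the severity order places atypical hyperplasia/EIN between malignant neoplasm and hyperplasia without atypia, which is the split that 9.6.1.1 already makes, and that this order governs the single-reader notice, the majority and the tie-break. Check the pre-specified majority rules against it. Send sites the majority diagnosis with its atypia subcategory. Follow-up decisions stay with the investigator as now.

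The cost is a short protocol change, with the approvals that 13.1 requires for an amendment, and a change to the central result template. No extra reader is needed, since every reader's diagnosis is already captured. The downside is possibly a few more notices or SAE reports. If the form and template already carry the subcategory, only the protocol text needs to change.

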9.6.3.1.5 Follow-up of endometrial biopsies with abnormalities

Endometrial biopsies with a safety-reader diagnosis (Part II of the evaluation form) other than “benign endometrium” (i.e. “Malignant neoplasm”, “Endometrial Hyperplasia” with or without atypia) should undergo an expedited multi-reader assessment. If an expedited multi-reader assessment is not possible (e.g. due to sample export regulations), follow-up procedures will be decided based on the safety-reader diagnosis.

Endometrial biopsies with a multi-reader majority diagnosis (Part II of the evaluation form) other than “benign endometrium” (i.e. “Malignant neoplasm”, “Endometrial Hyperplasia” with or without atypia) should be followed-up according to investigator¹⁹ assessment, i.e., either by performing endometrial biopsies, until resolution (i.e. until a follow-up biopsy shows a majority diagnosis of “Benign endometrium”) or by performing a therapeutic intervention as per local standard of care).

The timing of follow-up biopsies and/or possible therapeutic interventions according to local standard of care will be determined by the investigator (or by a gynecologist in case the investigator or sub-investigator is not specifically trained in gynecology) according to the observed abnormality. Typically, at least one endometrial shedding should have occurred before a follow-up biopsy is performed.

The follow-up biopsies should be performed within the study framework and evaluated by blinded multi-reader assessment. In case follow-up biopsies and/or other interventions are conducted at non-study sites, all efforts should be taken that results are obtained and documented appropriately.

For FUP of a majority diagnosis of “Benign endometrium – PAEC yes” please see Section [9.6.3.1.6](#).

For reporting of abnormal biopsy results as adverse event of special interest or SAE, please see Sections [9.6.1.6](#) and [9.6.1.4](#).

9.6.3.1.6 Follow-up of PAEC

Besides standard diagnostic criteria (i.e., proliferative/secretory/atrophic endometrium, endometrial hyperplasia) presence of PAEC will be analyzed in all endometrial biopsy samples as part of the multi-reader assessment. The diagnosis of PAEC is based on a constellation of histologic features that, taken together, are characteristic. None of the features is unique, and to some extent any may be seen in patients who have not been treated with PRMs. The common histologic features are endometrial glands showing cystic dilatation and an irregular architecture lined by inactive gland cells and compact, nondecidualized stroma.

If PAECs have been detected in the biopsy at the last visit before leaving the study (i.e. at the scheduled Safety closeout visit or at a premature discontinuation visit) according to the majority diagnosis resulting from the multi-reader assessment, the site will be informed and

¹⁹ or by a gynecologist in case the investigator or sub-investigator is not specifically trained in gynecology.

an additional FUP biopsy should be scheduled. In case PAEC findings are still present, the study site will be informed and an additional biopsy is to be taken to evaluate resolution, with the timepoint of this additional biopsy to be determined case-by-case. If needed, more than one repeated biopsy may be taken and analyzed, except for cases with PAEC already present in the pre-treatment biopsy.

9.6.3.1.7 Heavy menstrual bleeding / suspicious bleeding pattern

The study drug may lead to changes in bleeding pattern, mostly amenorrhea during treatment, but can also be associated with intermittent spotting or mild intermittent bleeding of short duration.

Because unusual bleeding patterns or unusually heavy menstrual bleeding can also be a sign of endometrial pathology, the subject should be instructed to report changes in bleeding pattern or bleeding volume that seem unusual to her (and does not resemble the subject's natural cycle or bleeding pattern). Further the site was asked to actively contact subjects who upon review of the ESD Item 4 have entered more than 10 consecutive days of bleeding (intensity of "mild" or more) during study drug intake (ie, during a treatment period). In case such unusual bleeding events are reported or are detected from the ESD (item 4) the subject should undergo immediate evaluation by the investigator. With the Safety closeout visit a review of the bleeding data entered during the temporary pause should rule out any suspicious bleeding that would need immediate evaluation.

Standard criteria for evaluation of unusual HMB or bleeding pattern identified from review of bleeding data reports by the subject during the temporary pause

As guidance the following occurrences should be considered for further evaluation in the context of unusual bleeding:

- Prolonged bleeding:
Evaluation should be initiated if
 - Prolonged bleeding is reported by the subject and/or
 - the subject entered more than 10 consecutive days of bleeding in the eDiary (ESD item 4, intensity of "mild" or more) with a maximum of 2 non-bleeding days in between.
- Continuous spotting:
Evaluation should be initiated if
 - Continuous spotting is reported by the subject and/or
 - if the subject entered more than 10 consecutive days of spotting in the e-diary with a maximum of 2 non-spotting in between.
- Unusual heavy bleeding:
Evaluation should be initiated if
 - Unusually heavy bleeding is reported by the subject

Evaluation plan for subjects with unusual HMB or bleeding pattern

The evaluation should include the following assessments:

- Unscheduled ultrasound (if bleeding abnormality is reported outside of visit with scheduled ultrasound)

- In case of HMB or prolonged bleeding, unscheduled blood sample to assess for anemia
- Possible contributing factors (eg, new concomitant medication, variability of disease, perception of increased HMB after period of amenorrhea)

An unscheduled endometrial biopsy should be conducted in case of

- Endometrial thickness (double layer) > 18 mm and/or
- Clinical suspicion of relevant endometrial pathology

Further follow-up measures will be determined by the outcome of the endometrial biopsy (see Section [9.6.3.1.5](#)).

HMB should be recorded as an AE only as specified in Section [9.6.1.6](#). If HMB fulfills the criteria of an SAE (see Section [9.6.1.2.1](#)), it should be reported as such. An appropriate treatment as per local standard of care (eg, curettage) is to be performed after an endometrial biopsy has been taken.

